Other AEs of interest include elevation in liver enzymes, which has limited some subjects' dosing. As such, liver function tests should be routinely monitored during the conduct of navitoclax studies.

Some investigators have reported QTc prolongation as non serious adverse events (Investigator's Brochure, 2011). Many of these subjects were heavily pretreated with cardiotoxic drugs. Based on nonclinical evaluation, it is unknown or unlikely that QTc prolongation is related to navitoclax administration; however, further clinical QTc investigation is planned. Additionally, metabolic changes such as hyperuricemia, hyperkalemia, and increased lactate dehydrogenase (LDH) values have been reported and are consistent symptoms of tumor lysis syndrome (TLS). One serious adverse event of TLS was reported; however, with continued treatment with prophylaxis, no further events of TLS have been reported. A treatment management strategy for subjects experiencing TLS is discussed in Section 6.

The following recommended phase 2 doses (RP2D) were independently determined based on their respective safety and tolerability results:

- M06-814 (lymphoid malignancies): 7-day lead-in dose of 150 mg/day followed by 325 mg QD (21/21 days) (Wilson *et al.*, 2010).
- M06-822 (SCLC and other solid tumors): 7-day lead-in dose of 150 mg/day followed by 325 mg QD (21/21 days) (Gandhi *et al.*, 2011).
- M06-873 (CLL): 7-day lead-in dose of 100 mg/day followed by 250 mg QD

(21/21 days) (Roberts et al., 2012).

Clinical Pharmacokinetics

Pharmacokinetic (PK) data were obtained for the intermittent (14/21) dosing schedules in trials M06-814, M06-822, and M06-873, and for the continuous (21/21) dosing schedule in trial M06-873. M06-814 also tested for food effects on PK parameters. Overall, the absorption of navitoclax after oral dosing was relatively slow, with C_{max} achieved around 6-9 hours after first dose. Exposure (C_{max} and AUC₀₋₂₄) was approximately dose-proportional over a range of doses from 10 mg/day through 475 mg/day. There were no significant differences in PK values between disease groups (general lymphoid malignancies, SCLC, and CLL) (Investigator's Brochure, 2011). Individual study results are summarized below.

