 - Because the composition, PK, and metabolism of many herbal supplements are unknown, the concurrent use of all herbal supplements is prohibited during the study (including, but not limited to, St. John's wort, kava, ephedra [ma huang], ginkgo

- biloba, dehydroepiandrosterone [DHEA], yohimbe, saw palmetto, or ginseng).
- Due to the expected dose-limiting toxicity of thrombocytopenia, the following concomitant medications are not allowed during navitoclax administration: Warfarin, clopidogrel (Plavix), ibuprofen, tirofiban (Aggrastat), and other anticoagulants, drugs, or herbal supplements that affect platelet function are excluded, with the exception of low-dose anticoagulation medications (such as heparin) that are used to maintain the patency of a central intravenous catheter. Aspirin will not be allowed within 7 days prior to the first dose of navitoclax or during navitoclax administration. However, subjects who have previously received aspirin therapy for thrombosis prevention may resume a low dose (*i.e.*, maximum 100 mg QD) of aspirin if platelet counts are stable (≥50,000/mm³) through 6 weeks of navitoclax administration. All decisions regarding treatment with aspirin therapy will be determined by the investigator in conjunction with the medical monitor.
- 3.2.8 Preclinical studies indicate that navitoclax is metabolized by CYP3A4, is a moderate inhibitor of CYP2C8, and is a strong inhibitor of CYP2C9. Therefore, caution should be exercised when dosing navitoclax concurrently with CYP2C8 and CYP2C9 substrates. Common CYP2C8 substrates include paclitaxel, statins, and glitazones, whereas CYP2C9 substrates include phenytoin and warfarin. When possible, investigators should switch to alternative medications or monitor the patients closely (particularly in the case of medications that have a narrow therapeutic window such as warfarin. Use of warfarin is specifically prohibited while on study). CYP3A inhibitors such as ketoconazole and clarithromycin are not allowed 7 days prior to the first dose of navitoclax or during navitoclax administration.

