5.3.2 Navitoclax

Potential issues with navitoclax include drug-drug interactions and thrombocytopenia. See the navitoclax supportive care guidelines (Section 6) currently included in all company-sponsored protocols for managing thrombocytopenia (with platelet transfusion recommendations), lymphopenia, and tumor lysis syndrome.

In adult monotherapy clinical studies, reductions in circulating platelet counts were observed in an expected, dose-dependent predictable manner, with the nadir occurring 3-5 days after the first dose of navitoclax followed by a subsequent recovery during ongoing dosing. This effect is reversible with interruption of study drug. Platelets recover towards baseline with continued dosing, but may not necessarily reach baseline levels. **Therefore, adequate platelet monitoring should be obtained, including after initiation of navitoclax therapy and when platelet counts are noted to be <50,000/mm³ (see also Section 6.2).** Attenuated lead-in dosing appears to ameliorate the risk of early grade 4 thrombocytopenia, and continuous dosing

mitigates major swings in circulating platelet counts.

Colony stimulating factors (G-CSF, GM-CSF) or human erythropoietin will be considered during administration of navitoclax if deemed necessary by the investigator.

The following concomitant medications are not allowed during navitoclax administration due to mechanistic-based platelet toxicities from navitoclax: Warfarin, Clopidogrel (Plavix), ibuprofen, tirofiban (Aggrastat), and other anticoagulants, drugs, or herbal supplements that affect platelet function. Administration of heparin to keep subject's infusion lines patent is allowed. Low-dose anticoagulation medications that are used to maintain the patency of a central intravenous catheter are allowed.

Aspirin will not be allowed within 7 days prior to the first dose of navitoclax or during navitoclax administration. However, subjects who have previously received aspirin therapy for thrombosis prevention, may resume a low dose (*i.e.*, maximum 100 mg QD) of aspirin if platelet counts are stable (≥50,000/mm³) through 6 weeks of navitoclax administration. All decisions regarding treatment with aspirin therapy will be determined by the investigator in conjunction with the medical monitor.

Disulfiram is not allowed due to potential drug interactions.

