Navitoclax is a moderate inhibitor of the activity of cytochrome P450 (CYP) isoenzyme CYP2C8 (IC₅₀ = 3.4 μ M or 3.3 μ g/mL) and is a potent inhibitor of CYP2C9 activity (IC₅₀ = 1.0 μ M or 0.97 μ g/mL). At the expected biologically effective plasma concentration of about 3 to 5 μ M (3–5 μ g/mL), navitoclax is likely to inhibit the metabolism of drugs that are substrates for CYP2C8 and CYP2C9. Clinically relevant CYP2C8 substrates include paclitaxel, statins, and glitazones, whereas phenytoin and warfarin are substrates of CYP2C9. Co-dosing with CYP2C8 and CYP2C9 substrates should be undertaken with caution.

Navitoclax is metabolized in the liver by CYP3A4. Strong CYP3A4 inducers/inhibitors are NOT allowed. Weak or moderate inhibitors/inducers are allowed, but should be used with caution. CYP3A4 inhibitors such as ketoconazole and clarithromycin are not allowed 7 days prior to the first dose of navitoclax or during navitoclax administration.

5.4 **Duration of Therapy**

In the absence of treatment delays due to adverse event(s), treatment may continue until one of the following criteria applies:

- Disease progression,
- Intercurrent illness that prevents further administration of treatment,

- Unacceptable adverse event(s),
- Patient decides to withdraw from the study, or
- General or specific changes in the patient's condition render the patient unacceptable for further treatment in the judgment of the investigator.
- The study reaches its planned stopping date, which will be 2 years after the last patient's first dose of study drugs. However, in the event that a patient or patients have an excellent response to therapy that is ongoing at the time of this planned stopping date, the possibility of continuing treatment for the patient(s) in question will be subject to discussion.

5.5 **Duration of Follow Up**

Patients will be followed until the resolution or stabilization of all study-related toxicity and for a minimum of 30 days after removal from study or until death, whichever occurs first. Patients removed from study for unacceptable adverse event(s) will be followed until resolution or stabilization of the adverse event.

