Route(s) **of Administration:** Oral.

Method of Administration: Take navitoclax tablets with food.

Potential Drug Interactions:

CYP-mediated DDI: Navitoclax metabolizes via CYP3A4. Concomitant use of strong and moderate CYP3A4 inhibitors/inducers should be taken with caution. Use alternative medications if possible.

In vitro studies, navitoclax is a moderate inhibitor of CYP2C8, a strong inhibitor of CYP2C9 and a weak inhibitor of CYP2C19, CYP2D6 and CYP3A4 following a 300 mg QD dose. Use caution when navitoclax is administered with sensitive substrates of CYP2C8 and CYP2C9.

Navitoclax is not an inducer of CYP1A2, CYP2B6, CYP2C9 and CYP3A4 and therefore is not expected to have any potential for DDI via CYP. As for M13, it did not increase CYP1A2, CYP2B6 and CYP3A4 mRNA expression when tested at concentrations up to 30 μM.

Transporter mediated DDI: Navitoclax and M13 (navitoclax metabolite) are inhibitors of OATP1B1/3, with IC₅₀ values of 2.0 μ M (navitoclax) and 20.8 μ M (M13) but do not result in DDI based on the static model (OATP1B1/1B3, R<1.1). Navitoclax may inhibit P-gp and BCRP at therapeutic doses (I_{gut}/IC₅₀>10). Both navitoclax and M13 are P-gp and BCRP substrates but are not OATP1B1/3 substrates.

Navitoclax and M13 are not inhibitors of OCT1, OCT2, OAT1, OAT3, MATE1 or MATE2K. M13 is not an inhibitor of P-gp, BCRP, or BSEP in vesicles or in MDCK cells.

Plasma Protein Binding: Navitoclax was highly bound to plasma proteins across species. Protein binding was highest in the human and dog (99.99%) followed by the mouse, rat, and monkey (99.98%). For each species studied, the extent of binding was constant over the entire drug concentration range (10 to 500 μ g/mL) and the

binding was independent of gender. The results indicate that navitoclax will be highly bound (99.99%)

to proteins in human plasma at concentrations expected after a therapeutic dosage (Cmax of 6.5 $\mu g/mL$).

Patient Care Implications:

Women of child-bearing potential (WOCBP) and men must agree to use adequate contraception (hormonal or barrier method of birth control; abstinence) while on treatment with navitoclax (ABT-263) and at up to 30 days after the last dose of navitoclax (ABT-263). Male study subjects who are sexually active with a WOCBP (woman of child-bearing potential), even if the male subject has undergone a successful vasectomy, must agree to use condoms while on treatment and through at least 90 days after the last dose of study drug.

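### Section 8.1.2 lets strong CYP3A4 inhibitors and inducers be used with caution, while Section 5.3.2 prohibits them; strong inducers are prohibited nowhere else and have no washout

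*Combined protocol and SAP*

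**What the plan says.** Three places in the combined protocol and SAP set a rule for CYP3A4 co-medication with navitoclax.

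- **Section 3.2, criterion 3.2.8 (exclusion criteria):** "CYP3A inhibitors such as ketoconazole and clarithromycin are not allowed 7 days prior to the first dose of navitoclax or during navitoclax administration". No strength is stated, and inducers are not mentioned.
- **Section 5.3.2 (concomitant medication, navitoclax):** "Strong CYP3A4 inducers/inhibitors are NOT allowed", followed by "Weak or moderate inhibitors/inducers are allowed, but should be used with caution". The section then repeats the 3.2.8 sentence almost unchanged: same two example drugs, same 7-day period, same prohibition during dosing.
- **Section 8.1.2 (pharmaceutical information, navitoclax):** "Concomitant use of strong and moderate CYP3A4 inhibitors/inducers should be taken with caution", followed by "Use alternative medications if possible". Strong and moderate agents share one rule, and neither is prohibited.

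No clause in the supplied text says which section prevails.

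**The concern.** An investigator or pharmacist deciding whether a patient on navitoclax may take a strong CYP3A4 agent gets opposite answers from two sections. Section 5.3.2 prohibits the drug; 8.1.2 leaves it to judgement.

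This bears first on patient safety. Navitoclax is cleared through the enzyme in question, and Section 2.2.2 names thrombocytopenia as its primary dose-limiting toxicity. A strong inhibitor would be expected to raise navitoclax levels, and so the platelet risk. A strong inducer would be expected to lower them, so that the patient gets less exposure than the assigned dose implies. Section 1.1.2 makes confirming safety and tolerability at the recommended phase 2 dose a primary objective of Part 2, and Section 13.1.2.2 lists adverse events among its primary endpoints. The rule therefore still matters after dose finding.

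**Working it through.** No sample size, power or error rate enters this point. The check sets the three rules side by side and then follows the chain from enzyme to platelets.

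**1. The rules by type of agent**

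| Agent | 3.2.8 | 5.3.2 | 8.1.2 |
|---|---|---|---|
| Strong inhibitor | Prohibited (no strength stated), from 7 days before first dose and during dosing | Prohibited; same 7-day wording | Caution; alternatives if possible |
| Moderate inhibitor | Prohibited if the ungraded wording is taken literally | Allowed with caution, but the repeated prohibition is also ungraded | Caution; alternatives if possible |
| Weak inhibitor | As for moderate | As for moderate | Not addressed |
| Strong inducer | Silent | Prohibited; no washout given | Caution; alternatives if possible |
| Moderate inducer | Silent | Allowed with caution | Caution; alternatives if possible |
| Weak inducer | Silent | Allowed with caution | Not addressed |

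Reading across the rows:

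- **Strong inhibitors:** 8.1.2 stands against both other sections.
- **Strong inducers:** 8.1.2 stands against 5.3.2 alone. No section gives a washout. This row has the widest gap.
- **Weak or moderate inhibitors:** the ungraded sentence in 3.2.8, repeated in 5.3.2, does not sit easily with the allowance in 5.3.2 itself. This is an ambiguity and secondary to the two rows above.

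**2. Why the conflict matters for exposure and platelets**

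- Enzyme: "Navitoclax is metabolized in the liver by CYP3A4" (5.3.2).
- Dose to exposure: Cmax and AUC over 24 hours "was approximately dose-proportional over a range of doses from 10 mg/day through 475 mg/day" (2.2.2).
- Dose to platelets: "reductions in circulating platelet counts were observed in an expected, dose-dependent predictable manner" (5.3.2, adult monotherapy studies).

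Together these support a direction: more exposure with inhibition and more platelet reduction; less exposure with induction.

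**3. What can be said about size**

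The documents give no ratio of navitoclax AUC or Cmax with and without a CYP3A4 inhibitor or inducer. The change in exposure and in the thrombocytopenia rate therefore cannot be computed.

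The dose ladder in Table 5.1 gives a yardstick only. If exposure is proportional to dose, one navitoclax step corresponds to an exposure ratio of 200/150 = 1.33, 250/200 = 1.25, 300/250 = 1.20 or 325/300 = 1.08. Section 2.2.2 puts interpatient variability at about 40% to 46%. Whether a strong agent would move exposure by less than, about, or more than a step is not something these documents answer.

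**4. Where dose-limiting-toxicity decisions could still be touched**

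Section 5.1.1 ends escalation on Schedules A and B with Protocol Version 10 (8/9/16); the current version is dated July 22, 2022. Any effect on escalation is therefore limited to cohorts still escalating, which in the current text could only be on Schedule C.

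**The case against.** **The sections have different roles.** Section 8.1.2 is pharmaceutical information, 3.2.8 is an eligibility rule, and 5.3 governs concomitant medication. Section 4.2 requires every inclusion and exclusion criterion to be met before registration, so a site admitting a patient on a prohibited inhibitor would breach eligibility whatever 8.1.2 says. This stands for inhibitors at entry and narrows the problem. It does not reach inducers, which 3.2.8 omits. It is also weaker for drugs started on treatment, because no order of precedence is stated.

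**Section 8.1.2 discourages these drugs.** True, but a preference for alternatives is not a prohibition. For warfarin, 3.2.8 gives general advice and then adds an explicit prohibition; 8.1.2 adds none for strong CYP3A4 agents.

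**Safeguards exist.** Section 5.3.1, although written for trametinib, requires all concurrent drugs to be recorded and asks that the Principal Investigator be alerted to agents that may affect selected CYP450 isoenzymes. Section 3.2.8 requires counselling on interactions at enrolment. Sections 5.3.2 and 6.2.1.1 call for platelet monitoring, and 6.2.1.1 has navitoclax interrupted or discontinued when the pre-dose count is below 25,000/mm³. An affected patient would probably be identified. These measures limit the harm; they do not settle which rule applies.

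**Stronger readings that a reader might infer, and that the documents do not support:**

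- *That there are three separate rules.* Section 5.3.2 repeats the 3.2.8 inhibitor prohibition and washout, so those two sections largely agree on such inhibitors. The direct contradiction is 8.1.2 against the others.
- *That the dose-limiting-toxicity counts or the combination pharmacokinetics are contaminated.* Nothing shows that any patient took such a drug. Escalation on Schedules A and B is closed, and Section 9.3 plans serial sampling in Part 1 but only pre-dose samples in Part 2. That one patient can turn a decision in cohorts of 3 to 6 is true of any deviation and measures nothing specific to this one.
- *That the patient handout is wrong too.* The text of Appendix D was not available, so its wording cannot be judged.

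**Conclusion.** The contradiction is real: for a strong CYP3A4 inhibitor or inducer, following 8.1.2 as written permits what 5.3.2 prohibits. It is an internal inconsistency in a safety rule and implies no flaw in the statistical design.

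Its size is unknown. The direction of effect rests on three statements in the documents (metabolism by CYP3A4, approximate dose proportionality, dose-dependent platelet reduction) and on the assumption that inhibition and induction shift exposure in opposite directions. The platelet-safety concern is about inhibitors; for inducers the issue is altered exposure. Only patients who actually take such a drug are affected, and the documents do not say how many might. The correction is worth making because it is cheap and the rule protects against the drug's principal toxicity.

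**What to change.** The sponsor should reconcile criterion 3.2.8 and Sections 5.3.2 and 8.1.2 to a single rule, stated identically in each place, that:

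- covers both inhibitors and inducers;
- says what applies at each strength (strong, moderate, weak);
- uses the same washout wording in every section and makes clear whether a washout applies to inducers.

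Which rule is clinically right is for the sponsor to decide; nothing here favours one. The cost is wording in an amendment. Sample size, endpoints and analyses do not change.

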8.1.3 Agent Ordering and Agent Accountability

8.1.3.1 NCI-supplied agents may be requested eligible participating Investigators (or their authorized designee) at each participating institution. The CTEP-assigned protocol number must be used for ordering all CTEP-supplied investigational agents. The eligible participating investigators at each participating institution must be registered with CTEP, DCTD through an annual submission of FDA form 1572 (Statement of Investigator), NCI Biosketch, Agenda Shipment Form, and Financial Disclosure Form (FDF)

Submit agent request through the PMB Online Agent Ordering Processing (OAOP) application (https://ctepcore.nci.nih.gov/OAOP). Access to OAOP requires the establishment of a CTEP Identity and Access Management (IAM) (https://ctepcore.nci.nih.gov/iam) account and the maintenance of an "active" account status, a "current" password, and active person registration status. For questions about drug orders, transfers, returns, or accountability, call [contact]) or email PMB ([contact]) any time. Refer to the PMB's website for specific policies and guidelines related to agent management."

- 8.1.3.2 Agent Inventory Records The investigator, or a responsible party designated by the investigator, must maintain a careful record of the inventory and disposition of all agents received from DCTD using the NCI Drug Accountability Record Form (DARF). (See the NCI Investigator's Handbook for Procedures for Drug Accountability and Storage.
- 8.1.3.3 Brochure Availability The current versions of the IBs for PMB-supplied agents will be accessible to site investigators and research staff through the PMB Online Agent Order Processing (OAOP) application. Access to OAOP requires the establishment of a CTEP Identity and Access Management (IAM) account and the maintenance of an "active" account status and a "current" password, and active person registration status. Questions about IB access may be directed to the PMB IB coordinator at: [contact]

8.2 Other Investigational Agent(s)

N/A

8.3 Commercial Agent(s)

N/A

9. BIOMARKER, CORRELATIVE, AND SPECIAL STUDIES

9.1 Biomarker Studies and Patient Tumor Biopsies

9.1.1 Validation of KRAS and NRAS mutations

9.1.1.1 Rationale

To ensure the validity and accuracy of KRAS or NRAS mutations in patients enrolled in this study, KRAS and NRAS genotyping will be confirmed centrally at a single institution (Massachusetts General Hospital) using a standardized CLIA-approved clinical genotyping platform. For those patients whose KRAS or NRAS status was not determined initially by this platform, KRAS or NRAS mutation will be confirmed retrospectively using this standardized assay provided that tissue is available for analysis. However, patients will be allowed to enroll in the study prior to retrospective validation, provided they have a documented KRAS or NRAS mutation as determined by a CLIA-approved assay.

9.1.1.2 Procedures and Analysis

KRAS or NRAS mutational status will be confirmed using the CLIA-approved standard clinical genotyping platform used for routine clinical care at the Massachusetts General Hospital, the SNaPshot assay (Dias-Santagata *et al*, 2010). SNaPshot assay will be performed in the Molecular Pathology Laboratory at the Massachusetts General Hospital Cancer Center.

9.1.2 Pharmacodynamic analyses in paired pre-treatment and on-treatment tumor biopsies.

9.1.2.1 Rationale

This study will incorporate ancillary/exploratory pharmacodynamic analyses to evaluate the effects of trametinib and navitoclax given in combination on key cellular signaling pathways and on the induction of apoptosis and inhibition of tumor cell proliferation. Paired pre-treatment and on treatment (day 22 +/- 7 days) core biopsies will be obtained from all patients in the Phase 1b

schedule A portion of the trial, (day 15 +/- 7 days) in the schedule B or C portion, and the first 15 patients enrolled on the Phase 2 portion of the trial (minimum of 4 patients from each of cohorts 1, 2 and 3 will be biopsied), if these patients have lesions that can be safely biopsied without unacceptable risk or discomfort to the patient. Biopsies from patients in the Phase 1b portion of the trial will provide an evaluation of the effects of each cohort's dose level on signaling pathway inhibition, inhibition of tumor cell proliferation, and induction of tumor cell death. This will provide an important metric as to the extent of target inhibition at each given dose level. Paired biopsies obtained from the first 15 patients enrolled in the Phase 2 portion of the trial (minimum of 4 patients from each of cohorts 1, 2 and 3 will be biopsied) will provide a more detailed assessment of the pharmacodynamic effects of therapy at the RP2D and will offer the potential to correlate pharmacodynamic effects with tumor response and patient outcome.

Previous studies incorporating pharmacodynamic analyses of targeted agents (including MEK inhibitors) given in combination have shown that the degree of target and/or pathway inhibition achieved at doses of targeted agents reachable when given in combination (which are often less than the doses achievable when given as single agents, due to additive toxicity) can be incomplete, and thus inadequate to promote efficacy (Speranza et al., 2012). Thus, it will be critical to understand the degree of target and/or pathway inhibition achieved at a given dose level of the combination and at the RP2D, as this may have important implications on the efficacy observed.

